## SPECIFIC AIM

1. To identify dose-dependent changes in brain networks using fMRI studies in healthy volunteers receiving nitrous oxide.
2. To identify dose dependent changes in brain feedback connectivity using EEG in healthy volunteers receiving nitrous oxide.

## METHODOLOGY

Here we describe a mechanistic study in healthy human volunteers to achieve the objectives of our specific aims.

*Participant Recruitment:* We will recruit 25 individuals for an fMRI/EEG study.

Healthy volunteers will be identified through the UM Clinical Studies website (<http://www.umclinicalstudies.org>) for research volunteers. We will also utilize the Minority Health Research Program (MHRP) to help recruit minorities into our study. Our goal is to recruit groups of subjects that are representative of the southeastern Michigan population. (See Appendix A for ethnic and racial targeted enrollment). All interested volunteers will first contact [name] or the study coordinator for a preliminary screen to determine if the subject meets the inclusion/exclusion criteria and that the subject understands the research study. Specifically, the screening script will be read to potential participants, after which, they will be screened over the phone for eligibility using phone screening questionnaires. All screening documents have been attached to the Subject Recruitment section of the IRB application. [name] or the study coordinator will also answer any questions that the potential participants may have at this time. If the potential participant responds to the psychosis, the mood disorder, or the Patient Health Questionnaire-9 (PHQ-9) depression screening questionnaire in

a manner that would potentially indicate a depressive/mood diagnosis, he/she will be referred to the Depression Center at the University of Michigan Health System ([name]). Eligible participants will then be scheduled to participate. [name] and the study coordinator are responsible for obtaining full written informed consent on the day of the first study visit upon the participant's arrival. Privacy will be maintained throughout the screening process per normal UMHS HIPAA privacy policies.

Study participants:

*Inclusion criteria* include: age 21-40, right-handed, American Society of Anesthesiologists Class 1 physical status, body mass index <30, with Mallampati 1 or 2 airways.

*Exclusion criteria* include: history of obstructive sleep apnea, history of difficult airway with previous anesthetics, gastroesophageal reflux, hypertension or other cardiovascular abnormalities, pulmonary hypertension, history of drug use, history of chronic alcohol abuse, history of pain disorders, history of depression, psychosis or bipolar disorder, history of seizures or other neurologic disorders, history of methylenetetrahydrofolate reductase deficiency (a contraindication for nitrous oxide), history of known hypersensitivity to midazolam, Zofran, labetalol or glycopyrrolate, pregnant and / or nursing mothers, contraindications to the neuroimaging methods used (i.e. metal implants), tattoos in the head/neck region (all other tattoos may be subject to study exclusion by investigators), and any impairment, activity, or situation – as determined by the study coordinator or primary investigators – that would prevent satisfactory completion of the study protocol.

*Power analysis:* We calculated power using data from fMRI analyses. Based on an effect size (Cohen's *d*) derived from preliminary data, 22 participants are required for a 90% power to detect a statistically significant reduction in average path length (reflecting network efficiency). In case of drop out across, we will continue to recruit until we have 22 volunteers with completed data sets.

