All subjects will have MR-compatible EEG electrodes affixed to their scalp for monitoring during the study. Participants will first complete an altered states of consciousness questionnaire. Continuous EEG will be acquired during a baseline (rest) period followed by three additional tasks mentioned previously.

For each participant, these tasks will be repeated at a low dose of nitrous oxide that is normally associated with analgesia (35% inhaled concentration) and a higher dose of nitrous oxide that is associated with anesthesia. Following administration of the analgesic dose of nitrous oxide, participants will be asked to complete a questionnaire to assess altered states of consciousness. Each testing session will conclude with a 15-minute continuous EEG acquired during the participant's recovery of consciousness. Following testing, the participants will be asked to complete an altered state of consciousness questionnaire.

To maximize safety, nitrous oxide will be delivered using MRI-compatible anesthesia machines at the University of Michigan hospital, and anesthetic doses of nitrous oxide will be administered outside of the scanner, where airway patency and physiological stability will be established prior to imaging the state of anesthetic-induced unconsciousness. At least two fully-trained anesthesiologists will direct all anesthetic administration. In order to maximize clinical monitoring during emergence, recovery from anesthetic doses will occur outside of the MRI scanner as well. All participants will receive ondansetron (4mg IV) with an additional dose of dexamethasone (4mg IV) if needed to prevent nausea and vomiting. In addition, glycopyrrolate (0.42-0.4 mg IV), labetalol (5-10 mg/kg IV), and midazolam (1-2 mg IV) will be available for use to mitigate any side effects, as needed. Also, standard intraoperative monitors (electrocardiogram, pulse oximetry, capnography) will be used.

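### The hypersensitivity exclusion names four of the five IV drugs provided for the scanning visit and omits dexamethasone; the two lists should be reconciled

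*Combined protocol and SAP*

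**What the plan says.** Two places in the combined protocol and SAP bear on this.

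In METHODOLOGY, the exclusion criteria include a drug-specific item: "history of known hypersensitivity to midazolam, Zofran, labetalol or glycopyrrolate". The list ends with a discretionary item, left to the study coordinator or primary investigators, for circumstances "that would prevent satisfactory completion of the study protocol". The inclusion criteria are "age 21-40, right-handed, American Society of Anesthesiologists Class 1 physical status, body mass index <30, with Mallampati 1 or 2 airways". None of these concerns drug allergy.

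In EXPERIMENTAL PROTOCOL, the Scanning Visit text sets out the ancillary drugs in two consecutive sentences. The first covers antiemetics: "All participants will receive ondansetron (4mg IV) with an additional dose of dexamethasone (4mg IV) if needed to prevent nausea and vomiting". The second covers drugs held in reserve: "glycopyrrolate (0.42-0.4 mg IV), labetalol (5-10 mg/kg IV), and midazolam (1-2 mg IV) will be available for use to mitigate any side effects". The doses in these sentences are not part of this point.

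The same section says that "At least two fully-trained anesthesiologists will direct all anesthetic administration", and that medication during recovery is given as needed under monitoring by a trained anesthesiologist. On the content of screening, METHODOLOGY says only that "All screening documents have been attached to the Subject Recruitment section of the IRB application".

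**The concern.** The authors chose to screen for hypersensitivity by naming the drugs, and the names they chose cover every ancillary IV drug in the plan except one. That pattern looks like an oversight. No reason is given for treating dexamethasone differently.

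The stake is participant safety. These are healthy volunteers in a mechanistic study. The study coordinator checks eligibility against the criteria before consent. A volunteer with a known dexamethasone hypersensitivity meets every written criterion on this point and can go on to a visit at which the drug may be given. That visit includes a nitrous oxide level described as consistent with unconsciousness, so by the time an antiemetic is needed the participant may be poorly placed to volunteer an allergy history. Screening is the natural point at which to ask, and the plan already uses it for the other four drugs.

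**Working it through.** The plan states no figure on this point, and no sample-size or power calculation applies. The check is a comparison of two lists, followed by a search for any other written safeguard.

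**Step 1. Inputs.** The drugs provided are taken from the two Scanning Visit sentences in EXPERIMENTAL PROTOCOL. The drugs screened for are taken from the hypersensitivity item in the METHODOLOGY exclusion criteria. I take Zofran to be the brand name of ondansetron. The documents do not say so, but it is common drug nomenclature.

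**Step 2. Comparison.**

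| Drug provided (Scanning Visit) | Planned use | Named in the hypersensitivity exclusion |
|---|---|---|
| Ondansetron | All participants | Yes, as Zofran |
| Dexamethasone | If needed | No |
| Glycopyrrolate | As needed | Yes |
| Labetalol | As needed | Yes |
| Midazolam | As needed | Yes |

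Provided: 2 antiemetics + 3 reserve drugs = 5. Named in the exclusion: 4. Missing: 5 − 4 = 1, which is dexamethasone. The exclusion names no drug that is absent from the provided list, so the lists differ in this one respect only.

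**Step 3. Can conditional use explain the omission?** Four of the five drugs are conditional: dexamethasone, glycopyrrolate, labetalol and midazolam. Three of those four are in the exclusion. Being given only when needed was therefore not a reason for leaving a drug out.

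**Step 4. Does another written provision close the gap?**

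- *Inclusion criteria.* They cover age, handedness, physical status class, body mass index and airway. They set no allergy requirement.
- *Catch-all exclusion.* It turns on whether the volunteer can complete the protocol. Someone with this hypersensitivity can complete every scan and task without needing dexamethasone, so the clause does not clearly apply. It is also a matter of discretion.
- *Anesthesiologist contact before scanning.* At the consent/pre-scan visit this is described as a brief airway assessment. No allergy review is mentioned.
- *Anesthesiologist direction during scanning and recovery.* It is stated, but no allergy check before dexamethasone is written.
- *Screening forms.* They are attached to the IRB application and are not reproduced, so their content is unknown.

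Dexamethasone is mentioned nowhere else in the documents.

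**Step 5. Size.** The group at risk is volunteers who both have a known dexamethasone hypersensitivity and turn out to need the drug. The documents give neither rate, so I put no number on it. With 25 volunteers to be recruited and a condition taken to be rare, the expected count is very small.

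**The case against.** The strongest reply is that the practical risk is remote. Dexamethasone is conditional. At least two trained anesthesiologists direct the anesthetic, and another or the same specialist monitors recovery. An experienced clinician would ordinarily be alert to a known allergy. The unseen screening forms may already ask about drug allergies. The criteria are also introduced as including the listed items and end in a discretionary one, so they are not worded as exhaustive. All of this stands, and it limits how much weight the point can bear. It does not remove the point: the two lists still disagree, and the protocol text has no written step that would catch the case.

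Three stronger readings are tempting, and the documents do not support them.

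- *That the gap threatens completed data sets.* A reader might infer that an allergy discovered on the scan day would cost a participant and force a replacement towards the 22 completed data sets. But the drug is only given if needed, no imaging or EEG procedure depends on it, and withholding it is within the plan. The inference also conflicts with the reading of the catch-all above: if the allergy did prevent completion, the catch-all would cover it.
- *That the number of participants likely to receive dexamethasone measures the risk.* It would measure exposure to the drug, not exposure of hypersensitive people. The documents give no rate of use from which to calculate even that. Likewise, one drug in five is a share of a list and not a probability of harm.
- *That allergy is not screened for at all.* The written criteria do not name this drug. What the phone questionnaire asks cannot be seen.

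**Conclusion.** The point holds as a specific inconsistency in a safety criterion. Five IV drugs are provided, four are named in the hypersensitivity exclusion, and dexamethasone is the one left out. Read as written, the criteria admit a volunteer with a known dexamethasone hypersensitivity, who could then be given it.

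It is a small point. The expected number affected is very small, and specialist administration makes the path from eligibility to harm indirect. It has no bearing on sample size, power, completed data sets or analysis. It is still worth correcting, because the participants are healthy volunteers and the correction is almost free.

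The conclusion rests on two things: that Zofran and ondansetron are the same drug, and that the written criteria are what the coordinator applies. If the screening forms already ask about dexamethasone or drug allergy in general, the practical gap narrows or closes, and what remains is an alignment of the protocol text.

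**What to change.** Reconcile the METHODOLOGY exclusion criteria with the Scanning Visit drug list so that the drugs named in the hypersensitivity exclusion and the drugs provided are the same set. Whether this is done through the criteria or through the drug list is a decision for the clinical team. Then confirm that the phone screening questionnaire held with the IRB application matches the agreed set, and align it if it does not.

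The cost is one line of protocol text, possibly one screening question, and at most a very rare extra screen failure. No procedure, staff time at the scanner or additional participant is needed.

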## STATISTICAL ANALYSIS

### Functional connectivity magnetic resonance imaging (fcMRI)

fcMRI will be performed as described in our previous publications. During fcMRI, participants will either be at rest or receiving a pain stimulus via a pressure cuff applied to the left lower leg evoking tonic pressure with pain of 40 on a 100 point numerical rating scale (0=no pain; 100=worst pain imaginable). This sustained pain is relevant to deep musculoskeletal clinical pain and can be applied for long durations (i.e. minutes) without tissue damage. Data will be corrected for physiological effects such as cardio-respiratory fluctuations that are known to influence fcMRI estimation. Resting connectivity network analysis will be performed using the FSL (FMRIB's Software Library, [www.fmrib.ox.ac.uk/fsl](http://www.fmrib.ox.ac.uk/fsl)) software package. All data will be corrected for motion artifacts, smoothed (FWHM 5 mm), and high-pass temporal filtered ( $f = 0.006\text{Hz}$ ). ICA Approach. The within- and between-subject resting fMRI data analysis will be performed using ICA through Multivariate Exploratory Linear Optimized Decomposition into Independent Components (MELODIC, an FSL tool) and a previously validated dual regression approach. We will apply probabilistic ICA to identify global, independent patterns of functional connectivity existent in the entire subject population. The number of independent components will be limited to 25 to reduce subcomponents. Networks of interest will be selected and the spatial independent component maps identified from the population data will be used as a spatial regressor in a general linear model of the subject's resting fcMRI data. This will allow us to estimate subject-specific spatial maps for each component. These maps will then be passed up to group analysis. Seed-voxel Approach: We will evaluate functional connectivity using seed-voxels from brain regions previously shown to be involved in consciousness or pain. The average time course in these regions will be used as regressors in a whole brain general linear model to find other brain regions also correlated with the seed region. A whole brain general linear model will be performed using the seed time course, averaged over a 3 mm radius sphere, as the regressor of interest. The resulting single subject maps will be normalized to standard space and passed up to group analyses. fcMRI group analyses: Nitrous oxide effects on brain connectivity will be estimated using a factorial model with treatment (nitrous versus placebo) and time (pre versus post) as factors. All statistical maps will be corrected for multiple comparisons on the cluster level  $p < 0.05$ , derived from an uncorrected  $p < 0.001$  on the voxel level.

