
### Network Analysis

In terms of network properties to be analyzed, the **degree** is the number of connections a node (in this case, a given brain region) has, while the **modularity** is a measure of the extent to which the connected regions form individual functional modules. We will first investigate the characteristic modules

corresponding to different states, then quantify the modularity of the networks. High-degree **hubs** facilitate “shortcuts” of network information transmission (much like a hub airport facilitates travel shortcuts) and are identified with the measures of *centrality* in a network. The centrality of a node measures its relative ability to integrate information globally within a brain network. We will assess several centrality measures (degree centrality, closeness centrality, betweenness centrality and Eigenvector centrality) to test the robustness of the hub structure. The **average path length**, which measures the mean number of steps along the shortest paths for all possible pairs of network nodes, will be used for quantifying the **global efficiency** of brain networks (since efficiency varies inversely with path length). Network measures will be compared across states (waking, analgesia, anesthesia) using a repeated measures two-way analysis of variance (ANOVA) and a post hoc Tukey multi-comparison test (behavioral state as the within-subjects factor, anesthetic agent as the between-subjects factor). A p value <0.05 will be considered significant.

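### No network measure is named primary, and modularity, path length and up to four centralities share an unadjusted 0.05 threshold with no correction across measures

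*Combined protocol and SAP*

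**What the plan says.** The Network Analysis section lists modularity, average path length (used to quantify global efficiency) and a set of centralities: "We will assess several centrality measures (degree centrality, closeness centrality, betweenness centrality and Eigenvector centrality". The centralities are included "to test the robustness of the hub structure". The measures are compared across three states by repeated-measures ANOVA with "a post hoc Tukey multi-comparison test", and the section closes with "A p value <0.05 will be considered significant". The model is described as having "behavioral state as the within-subjects factor, anesthetic agent as the between-subjects factor".

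The only other multiplicity statement is in the fcMRI section: "All statistical maps will be corrected for multiple comparisons on the cluster level". It concerns voxel maps, not graph measures.

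The power analysis, under Methodology, says that "22 participants are required for a 90% power to detect a statistically significant reduction in average path length (reflecting network efficiency". It attributes this to a Cohen's d from preliminary data but gives neither the value nor the dose, contrast or sidedness. Path length and efficiency move in opposite directions, "since efficiency varies inversely with path length". The Objective and Expected Outcomes sections predict higher efficiency at the low dose and lower efficiency at the higher dose.

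**The concern.** Several outcomes are each judged at 0.05 and none is singled out, so a chance result on any of them could be reported as the network effect of nitrous oxide. Tukey does not protect against this, because it works within one measure at a time. The cluster correction does not either, because it applies to maps. What is at stake is the false-positive rate of the network conclusion. Power for path length itself is unaffected.

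A second, smaller matter is that a reader cannot tell which dose contrast the 90% refers to, although opposite changes are predicted at the two doses.

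**Working it through.** **Inputs from the plan.** 22 completers, 90% power and average path length (power analysis). Three states, p < 0.05, ANOVA with Tukey, and the list of measures (Network Analysis). Degree is not counted apart from degree centrality, nor efficiency apart from path length. That leaves 1 (modularity) + 1 (path length) + 4 (centralities) = 6.

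**Assumed, not in the plan.** The correlation between measures, varied from 0 to 0.9, and, for the count of six, that each centrality is reduced to one number per participant and state.

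**Step 1: the plan's own figure.** The 22 cannot be reproduced because d is not given. It can only be solved backwards. For a paired t test with n = 22 (21 df, noncentrality d√22) at 0.05, 90% power requires d = 0.725 two-sided or d = 0.645 one-sided. The 22 is therefore attainable, and it can be neither confirmed nor refuted.

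**Step 2: which corrections reach the network measures.**
- Tukey: between states, within one measure.
- Cluster-level correction: statistical maps only.
- Across modularity, path length and the centralities: none stated.

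**Step 3: false positives under independence.** P(at least one) = 1 − 0.95^k.
- k = 2 (modularity, path length): 1 − 0.9025 = 0.0975.
- k = 6: 1 − 0.735 = 0.265.

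**Step 4: allowing for correlation.** Simulated three-state repeated-measures F tests, n = 22, all measures null and equicorrelated, 40,000 trials:

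| Correlation | Any of 2 | Any of 6 | Holm over 6 |
|---|---|---|---|
| 0 | 0.094 | 0.266 | 0.048 |
| 0.5 | 0.091 | 0.213 | 0.044 |
| 0.8 | 0.078 | 0.145 | 0.030 |
| 0.9 | 0.071 | 0.111 | 0.022 |

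Counting any Tukey-significant pair instead of the overall F test gives nearly the same any-of-six results (0.266, 0.216, 0.146 and 0.113).

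**Step 5: direction.** A shorter path means higher efficiency, so the powered reduction matches the low-dose prediction. Expected Outcomes says that this prediction is based on preliminary data. The one preliminary nitrous oxide result given with a dose, lower efficiency at 60%, matches the high-dose prediction. The passages are compatible. What is missing is the dose behind d. If it was the low dose, the high-dose prediction has no power statement.

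**The case against.** **Path length is already the lead measure in practice.** It is the only one powered, and naming it would mostly make explicit what the power analysis implies. This stands, and it is why the fix is cheap. But the analysis section gives it no precedence, so the rule as written still treats all measures alike.

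**Six is a generous count.** The centralities are described as a check on hub structure, and centrality is defined for a node, so one number per participant is an assumption. Directional predictions for graph measures are made only for modularity and efficiency. This also stands: 11-27% is the upper reading and 7-10% the firmer one.

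**This is a mechanistic volunteer study, and its hypothesis needs a pattern of opposite changes at two doses.** A single chance result would not reproduce that pattern. This softens the consequence but does not remove it, since the plan sets a significance threshold for each measure and does not require the pattern.

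**Two stronger readings are tempting.** A reader might infer that the power paragraph contradicts the 60% result. That would follow only if d came from the 60% data, which nothing in the document says. A reader might also infer that the study is underpowered. If 22 came from an unadjusted paired test with d at the minimum that gives 90%, a Tukey-adjusted pair would have 80-83% power (d = 0.725) or 69-72% (d = 0.645). With d of 0.80-0.82 or more it would have 90%. The ranges reflect the choice of error term, which is unclear because the model names a between-subjects agent factor in a study of one agent. As d is unreported, these figures are not evidence of a shortfall.

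**Conclusion.** The multiplicity gap is real and modest. With no primary measure and no correction across measures, the false-positive chance is about 7-10% for modularity and path length together. It rises to about 11-27% if the four centralities are each tested as one number. These figures assume that all measures are null, and the ranges run from correlation 0.9 down to independence. The correlations are assumed, not taken from the trial.

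The power point is one of documentation only. The power paragraph omits d, its source dose, the contrast, the scan condition and the sidedness. Alpha and the test can be found in the Network Analysis section, but the power paragraph does not refer to them. Neither a contradiction in direction nor an error in the 22 is established.

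**What to change.** In the Network Analysis section:
1. Name average path length as the primary network measure at 0.05. Tie it to one scan condition (rest or cuff pain, the two that the fcMRI sections describe) and to the state contrast behind the power calculation. As sole primary it needs no adjustment across measures.
2. Control modularity and the centralities by Holm, or label the centralities exploratory robustness checks. Holm over all six gives a familywise error of about 2-5% in the table above. If path length is instead tested first at the full 0.05, proceed to the other measures, with Holm among them, only when it is significant. That order holds the whole set at 5%.

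In the power analysis:
3. State the d, the dose and data it came from, the contrast and the sidedness, and say which test in the Network Analysis section the 90% refers to.
4. If the figure is for the low dose, say that the opposite prediction at the higher dose has no power statement.

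The cost is a few sentences and stricter thresholds for the non-primary measures. No extra enrolment follows from this point.

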**APPENDIX A**

**ETHNIC / RACIAL TARGETED ENROLLMENT TABLE**

**Study Title: Network-Level Mechanisms of Nitrous Oxide in the Human Brain**

**Total Planned Enrollment: 22**

TARGETED/PLANNED ENROLLMENT: Number of Subjects			
Ethnic Category	Females	Males	Total
Hispanic or Latino	1	1	2
Not Hispanic or Latino	10	10	20
Ethnic Category: Total of All Subjects *	11	11	22
Racial Categories			
American Indian/Alaska Native	0	0	0
Asian	2	2	4
Native Hawaiian or Other Pacific Islander	0	0	0
Black or African American	2	2	4
White	7	7	14
Racial Categories: Total of All Subjects *	11	11	22

\* The "Ethnic Category: Total of All Subjects" must be equal to the "Racial Categories: Total of All Subjects."

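### Recruiting to 22 completed data sets and analysing three states by repeated measures ANOVA could exclude usable placebo and 35% runs from volunteers lost only at 70%

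*Combined protocol and SAP*

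**What the plan says.** - **Sample size** (METHODOLOGY, Power analysis). Twenty-two participants are said to give 90% power for a reduction in average path length. The effect size is a Cohen's d "derived from preliminary data", with no value given. Dropout is handled by replacement: "we will continue to recruit until we have 22 volunteers with completed data sets". The text does not define a completed data set, assume a dropout rate or cap enrolment.
- **Order of states** (EXPERIMENTAL PROTOCOL, Scanning Visit). Every volunteer receives placebo, then 35%, then 70%, and the scans are repeated at both doses.
- **Analysis of network measures** (STATISTICAL ANALYSIS, Network Analysis). Average path length and the other network measures are compared across the three states by repeated measures two-way ANOVA with Tukey comparisons. "A p value <0.05 will be considered significant"; sidedness is not stated. No analysis set or missing-data method appears.
- **Enrolment.** Participant Recruitment says "We will recruit 25 individuals for an fMRI/EEG study". Appendix A says "Total Planned Enrollment: 22".

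**The concern.** On the natural reading, a data set is complete only if the volunteer gets through 70%. A conventional repeated measures ANOVA also needs all three states from each person. Together these could leave out a volunteer whose placebo and 35% runs are sound but whose 70% run is missing.

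That matters for the contrast the sample size appears to serve. Network Analysis states that efficiency varies inversely with path length, and Expected Outcomes predicts higher efficiency at the low dose. A reduction in path length is therefore the predicted direction for 35% versus placebo, and that contrast does not use the 70% run. Restricting it to people who later complete 70% makes it conditional on a later event. If the more drug-sensitive volunteers are the ones lost, the 35% effect is understated. Replacing them restores the count of 22 but does not undo the selection.

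**Working it through.** **The plan's own figure.** The 22 cannot be reproduced, because neither d nor sidedness is given. Solving backwards for a paired t-test with n = 22 and 90% power:
- two-sided 0.05: the normal approximation is (1.960 + 1.282)/√22 = 0.691; the noncentral t gives d = 0.725;
- one-sided 0.05: d = 0.645;
- two-sided 0.05/3: d = 0.842.

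The two-sided 0.05 value is used below.

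**Bias if dropout depends on the 35% effect.** Assumptions: individual 35%-minus-placebo effects are standard normal about their mean (x in SD units, larger meaning a stronger effect), and the probability of loss at 70% is p(x) = 1/(1 + exp(−(a + bx))). The intercept a is set so that overall dropout, averaged over x, equals the stated rate. The completers' mean shifts by E[x(1 − p(x))]/E[1 − p(x)], and the relative bias is that shift divided by 0.725.

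| Overall dropout | Slope b per SD | Shift (SD) | Relative bias |
|---|---|---|---|
| 12% | 0.5 | −0.058 | −8% |
| 12% | 1 | −0.108 | −15% |
| 12% | 2 | −0.167 | −23% |
| 20% | 0.5 | −0.096 | −13% |
| 20% | 1 | −0.173 | −24% |
| 20% | 2 | −0.262 | −36% |

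The 12% is what 25 recruited and 22 complete would imply (1 − 22/25); the 20% is illustrative. At b = 0 the shift is zero.

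**Upper bound.** The worst case loses exactly the strongest responders. The shift is then φ(z)/(1 − q), with z the upper-q normal point: 0.227 SD at q = 12% (0.227/0.725 = 31%) and 0.350 SD at q = 20% (48%). The tabled values lie inside these limits.

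**Sensitivity to d.** For 12% dropout and b = 1, the relative bias is 0.108/0.645 = 17% with the one-sided d and 0.108/0.842 = 13% with the larger one.

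**Power of the completers' test, b = 1.** The SD among completers is about 0.959 at 12% dropout and 0.943 at 20%. The standardised effect becomes (0.725 − 0.108)/0.959 = 0.643, with power about 82%, and (0.725 − 0.173)/0.943 = 0.585, with power about 74%.

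**Precision alone.** If three of 25 are lost only at 70%, and for reasons unrelated to the effect, the standard error with all 25 is √(22/25) = 0.938 of that with 22, about 6% smaller. Power is about 93.5% against 90%.

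**Enrolment.** If each recruit completes independently, the chance that 25 recruits yield at least 22 completers is 0.65 at 12% loss and 0.23 at 20%. Open-ended recruitment could therefore readily pass 25.

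**The case against.** A reader might infer that the plan orders partial data to be thrown away. It does not. The Power analysis sentence is a recruitment target, and it names no analysis set. Exclusion is a consequence of that target combined with the usual behaviour of a repeated measures ANOVA when no other handling is given. This objection stands, and the point is limited to what the analysis could exclude.

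A reader might also extend the point to the whole analgesia hypothesis. That goes too far. The connectivity analyses (fcMRI group analyses) use a separate treatment-by-time factorial model, and the expected changes between pain regions and the default mode network are not governed by the three-state ANOVA.

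The mechanism is assumed. The documents give no rate, cause or timing of loss. Volunteers who leave before any gas add nothing to this contrast, and motion or equipment failure need not be related to drug effect. With about three expected losses the practical effect may be modest, and replacing dropouts is common in small volunteer studies. All of this stands and limits the size claimed. It does not justify an analysis that can lose sound runs without saying so.

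On enrolment, recruiting 25 to obtain 22 completers would be ordinary over-recruitment, so those two statements need not conflict, although the plan never links them. What remains is Appendix A's total of 22 against the 25 recruited, and the missing cap.

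**Conclusion.** The point holds for the network measures. As written, the recruitment target and the three-state ANOVA could exclude usable placebo and 35% runs and make that contrast conditional on completing 70%. Under the stated assumptions the completers' estimate is low by about 8%, 15% or 23% at 12% overall dropout, and 13%, 24% or 36% at 20%, for log-odds slopes of 0.5, 1 or 2 per SD. These are illustrations, since the rate, the slope and d are not in the documents. If dropout is unrelated to the effect, only precision is at stake: at most about 6% of the standard error in the three-of-25 case. None of this shows that 22 is the wrong sample size, which cannot be checked without d. The enrolment mismatch is real but clerical and secondary. The change is worth making because it is cheap and protects the contrast that the powered direction matches.

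**What to change.** 1. In Network Analysis, replace the repeated measures ANOVA with a linear mixed model with state as fixed effect and participant as random effect. Include every volunteer with at least one usable run, and keep the completers' analysis as a sensitivity analysis.
2. In Power analysis, define a completed data set. Commit to reporting how many volunteers are lost at each state and why.
3. Reconcile the enrolment figures across Participant Recruitment (25), Power analysis (22 completers) and Appendix A (22 in total), and state a maximum.

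The cost is wording and a corrected table, with no change to procedures and no participants beyond those the plan would already recruit. The downside is that the mixed model assumes data are missing at random given the observed runs. That fits loss at 70% predicted by the observed 35% response. It bears mainly on contrasts involving 70%, because a volunteer lost only there has both states of the 35% versus placebo contrast observed.
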